3.4 Protocol deviations

No Per-Protocol population is defined in this study and thus, no consideration with regards to deviations affecting such a population need to be considered. Nevertheless, for each interim analysis and final analysis, after all the data have been verified/coded/entered into the database, a review will be performed after last subject last visit. The purpose of this review will be to primarily check the quality of the data. The review will also help to decide how to handle problems in the subject's data (eg, missing values, withdrawals, dropouts, protocol deviations). In addition, the review will be used to identify the use of rescue therapy. The pre-analysis reviewers should ensure that the results of this review are communicated to the study team before locking the database.

After the pre-analysis review, resolution of all issues and documentation of all decisions, the database will be locked.

3.5 Analysis sets

The All Subject Population will include those subjects who are enrolled in the study. All available data entered into the database will be listed for this population.

The Safety Population will include all subjects enrolled who receive at least 1 injection of study treatment in this study. This population will be used to summarize the safety, PK, and immunological variables.

The Intention-to-Treat (ITT) Population will include all subjects irrespective of any protocol deviations who receive at least 1 injection of study treatment in this study and who have at least 1 efficacy measurement after the first injection of this study. This population will be used to summarize the efficacy variables.

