2.3 Study design and conduct

This is a Phase 2, open-label, multicenter study in children and adolescents with moderately to severely active CD who completed C87035, or were terminated from C87035 when the study was stopped by UCB, to assess the longterm safety and tolerability of CZP.

All subjects who complete Week 62 of C87035 or were terminated from C87035 when the study was stopped by UCB (and completed all assessments required for Week 62/Visit 23 at the time of termination) are eligible for entry.

Subjects may continue on CZP at the dose they were receiving at the end of C87035 (Low-Dose Group or High-Dose Group [weight adjusted in kg; see Section 7.2 and Table 7-1]) every 4 weeks until the subject reaches the age of 18 years or CZP is approved for use in the US by pediatric subjects with CD. The first clinic visit should coincide with the last visit of C87035 (Week 62/Visit 23). First study drug administration occurs 2 weeks later (Week 2) and subsequent clinic visits for safety and efficacy assessments are scheduled at 12-week intervals. After Week 2, subjects or parents/caregivers/appropriate designee as determined by the Investigator have the option of home administration of CZP upon appropriate training during a previous clinic visit(s) or continuing to have CZP administered every 4 weeks at the clinic. For subjects performing home administration, a phone call to the subject and/or the parents/caregiver will be performed by the Investigator (or designee) every 4 weeks between regular clinic visits in order to capture potential AEs and changes in concomitant medications, and to check compliance with home dosing. An SFU Visit will be conducted 12 weeks after the last dose of study medication for subjects.

Refer to Study Schedule of Assessments in Section 5.2 for visit-specific procedures and to Section 5.3 for a schematic representation of the study.

A DSMB will periodically review all emerging safety data (see Section 13.8). Based on the safety data, the DSMB can recommend modifying or stopping the study.

Loss of response/reinduction

- Subjects who were reinduced in C87035 are not eligible for reinduction in CR0012. Should loss of response occur in CR0012, the subject must be withdrawn.
- If there was no reinduction in C87035, 1 reinduction only is permitted in CR0012. If response is lost a second time in CR0012, the subject must be withdrawn.

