4.2 Handling of dropouts or missing data

For responder type variables, should a subject withdraw prior to completion of the study, then the subject will be classified as a nonresponder or nonremitter from and including the time of withdrawal.

A subject who does not have all the required data to derive a response status will be classified as a nonresponder or nonremitter at that particular time point.

If a subject receives rescue therapy or discontinues study treatment, then the subject will be classified as a treatment failure (nonresponder or nonremitter) from and including the time of the event, regardless of their score (PCDAI).

If a subject loses response and is reinduced, the subject will be classified as a nonresponder or nonremitter from and including the time of the reinduction.

In addition, for any other efficacy variables, no data will be used from and including the time of receiving rescue therapy in the summaries and analyses where relevant.

Unless part of an accepted imputation technique, any missing data during the study will remain missing.

If an AE has severity and/or relationship missing then the event will be assumed to be severe and/or highly probably related to the treatment.

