4.4 Examination of subgroups

No subgroup analysis for efficacy is planned since the total number of subjects participating in this study is small (n=16).

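### The ITT definition puts treated subjects with no post-injection efficacy measurement beyond the nonresponder rule, so if there are any, remission and response rates can only be biased upward

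*SAP*

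**What the plan says.** Two parts of the SAP decide who counts in the remission and response rates.

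- **Analysis set.** SAP 3.5 admits to the ITT set subjects who had an injection in this study and "who have at least 1 efficacy measurement after the first injection of this study". It adds: "This population will be used to summarize the efficacy variables". Protocol 13.1 has the same definition. The Safety Population in the same section needs only dosing: "all subjects enrolled who receive at least 1 injection of study treatment in this study".
- **Missing data.** SAP 4.2 says that a subject "who does not have all the required data to derive a response status will be classified as a nonresponder or nonremitter" at that time point. On withdrawal it says: "should a subject withdraw prior to completion of the study, then the subject will be classified as a nonresponder or nonremitter", from the time of withdrawal onward. SAP 9 repeats both rules for the efficacy summaries.

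The proportion in clinical remission is the main efficacy variable in Protocol 4.2. SAP 9 reports remission and response as number, percentage and 95% confidence interval.

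**The concern.** The two rules treat the same subject in opposite ways. Take a subject who is dosed and then contributes no efficacy measurement. Under SAP 4.2 and 9 that subject is a nonremitter at every later visit. Under SAP 3.5 the subject is not in the set to which that rule is applied.

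The schedule leaves room for this. The first injection is at Week 2 and the first scheduled PCDAI after it is at Week 14, so there are 12 weeks in which a subject could be lost without one unless an Early Termination visit takes place. Protocol 6.3 itself provides for loss to follow-up.

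Membership of the set is also unclear, because neither document says what an efficacy measurement is. If the term means PCDAI, a subject lost before Week 14 without a termination visit is out. If it means any listed efficacy variable, much less would qualify. SAP 3.1 does not settle this, since it bases denominators on whatever number suits the analysis. Under SAP 3.4 the review that decides how to handle missing values and dropouts comes after last subject last visit. In an open-label study, outcomes could be known by then.

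At stake is a shift of a few percentage points, in one direction only, in the main efficacy variable.

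**Working it through.** The plan gives no expected remission rate, sample size calculation or count of subjects in the ITT set, so there is no planned figure to reproduce. The effect can only be bounded.

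**Inputs from the documents**

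- Participants: 16 (SAP 4.4).
- First injection: Week 2 (SAP 2.3).
- PCDAI after that: every 12 weeks from Week 14, and at the Completion/ET visit (Protocol 10.1).
- Status of a treated subject with no later data: nonremitter (SAP 4.2 and 9).

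**Assumptions not in the documents**

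- All 16 were dosed.
- Percentages are taken over the whole analysis set, as the nonresponder rule implies.
- The number excluded, k, is 0 to 3.
- The number of remitters, x, is 4, 8 or 12, as a range.

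**Formula.** With every treated subject in the denominator the rate is x/16. With k excluded it is x/(16 − k), because excluded subjects would all be nonremitters and x is unchanged. The shift is

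x/(16 − k) − x/16 = kx / [16(16 − k)],

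which is never negative and is zero when k = 0 or x = 0. The relative increase is 16/(16 − k): 1.067, 1.143 and 1.231 for k = 1, 2 and 3.

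| Remitters x | All treated (k = 0) | k = 1 | k = 2 | k = 3 |
|---|---|---|---|---|
| 4 | 4/16 = 25.0% | 4/15 = 26.7% (+1.7) | 4/14 = 28.6% (+3.6) | 4/13 = 30.8% (+5.8) |
| 8 | 8/16 = 50.0% | 8/15 = 53.3% (+3.3) | 8/14 = 57.1% (+7.1) | 8/13 = 61.5% (+11.5) |
| 12 | 12/16 = 75.0% | 12/15 = 80.0% (+5.0) | 12/14 = 85.7% (+10.7) | 12/13 = 92.3% (+17.3) |

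The shift is largest when everyone left in the set is a remitter. It is then k/16: 6.25 points for k = 1, 12.5 for k = 2 and 18.75 for k = 3.

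**Against the precision.** The exact (Clopper-Pearson) 95% interval is 24.7% to 75.3% for 8/16 and 26.6% to 78.7% for 8/15. The first is 75.3 − 24.7 = 50.6 points wide, against a shift of 3.3.

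**By dose group.** SAP 9 also reports efficacy by dose group, where one subject weighs more. If a group had 8 subjects (an assumption), one exclusion would move 4/8 = 50.0% to 4/7 = 57.1%.

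**The case against.** The strongest reply is that the excluded group may be empty. PCDAI, ESR and CRP are all collected at the Completion/Early Termination visit (Protocol 8.5), so an early withdrawal who attends it stays in. Protocol 6.3 asks for documented efforts to obtain a final evaluation from subjects lost to follow-up. Concurrent medical procedures are a listed efficacy variable (SAP 2.2.2.3), recorded at every visit and phone contact (Protocol 10.10). On a literal reading, a Week 6 call could bring a subject into the set. All of this stands, and it limits the likely size. It also means that membership depends on how one undefined term is read.

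A reader might infer that the ITT definition cancels the nonresponder rule. It does not. Inside the set the rule applies in full to missed visits, incomplete PCDAI, withdrawal, rescue and reinduction. Only subjects with no post-injection efficacy measurement escape it.

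A reader might also infer that exclusion depends on outcome, in the sense that those lost early were not in remission. The documents do not show this: withdrawal can follow pregnancy, noncompliance or personal choice. The upward direction does not rest on it, though. It follows from the SAP's own choice to count such subjects as failures whatever the reason.

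Two further replies have weight. Efficacy is a secondary objective, and SAP 4.1 rules out inferential statistics for it. And a reader could probably find an omitted subject, because SAP 5.1 tabulates disposition for the Safety Population and SAP 3.5 lists all data for everyone enrolled. However, SAP 5.1 does not ask for the number excluded from the ITT set, and a wide interval is no reason to keep an avoidable bias.

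**Conclusion.** The conflict is real and narrow. SAP 3.5 removes from the efficacy denominator the very subjects whom SAP 4.2 and 9 would count as nonremitters. Measured against the SAP's own rule, any effect on remission or response can only be upward.

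It would go too far to say that the reported rate is inflated. Nothing in the documents shows that any of the 16 subjects is excluded, and with none excluded the ITT and Safety sets coincide. If one is excluded, and all 16 were dosed, the gain is 1.7 points with 4 remitters, 3.3 with 8 and 5.0 with 12, and never more than 6.25. That is small beside the interval, and no test, threshold or decision depends on it. The point is worth acting on because the bias runs one way, touches the main efficacy variable and can be removed cheaply.

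**What to change.** In SAP 3.5 and 9, state that remission and response are summarized in all subjects with at least 1 injection, that is, the Safety Population, and that the nonresponder rule of SAP 4.2 applies to every one of them. For continuous variables, report the number of subjects with data at each visit. Record this as a change from Protocol 13.1, which has the same ITT definition, so that the two documents do not simply disagree.

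The cost is a sentence or so in each of the two SAP sections and one documented deviation from the protocol. It needs no new data and no new analysis set. The rate may become slightly less favourable.

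If the ITT set is kept instead, the minimum is to define what counts as an efficacy measurement and to report how many treated subjects were excluded. That makes the problem visible but does not remove it.

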3.6 Center pooling strategy

No pooling of centers is planned for this study.

3.7 Coding dictionaries

All AEs and medical history will be coded and classified by primary System Organ Class (SOC) and Preferred Term (PT) according to Version 20.1 of the Medical Dictionary for Regulatory Activities (MedDRA®).

All medications will be coded using World Health Organization Drug Reference List (WHO-DRL). Medical procedures will not be coded.

4 STATISTICAL/ANALYTICAL ISSUES

4.1 Adjustments for covariates

No inferential statistics will be performed for the efficacy analysis. However, descriptive statistics for clinical response and clinical remission will be presented by subgroup variables of interest as defined in Section 4.4.

4.2 Handling of dropouts or missing data

For responder type variables, should a subject withdraw prior to completion of the study, then the subject will be classified as a nonresponder or nonremitter from and including the time of withdrawal.

A subject who does not have all the required data to derive a response status will be classified as a nonresponder or nonremitter at that particular time point.

If a subject receives rescue therapy or discontinues study treatment, then the subject will be classified as a treatment failure (nonresponder or nonremitter) from and including the time of the event, regardless of their score (PCDAI).

If a subject loses response and is reinduced, the subject will be classified as a nonresponder or nonremitter from and including the time of the reinduction.

In addition, for any other efficacy variables, no data will be used from and including the time of receiving rescue therapy in the summaries and analyses where relevant.

Unless part of an accepted imputation technique, any missing data during the study will remain missing.

If an AE has severity and/or relationship missing then the event will be assumed to be severe and/or highly probably related to the treatment.

4.3 Interim analyses and data monitoring

A DSMB reviews CR0012 safety data on an annual basis and can recommend modifying or stopping the study.

No formal interim analyses are planned. Should a regulatory authority request an interim analysis, this analysis will be performed according to the request.

4.4 Examination of subgroups

No subgroup analysis for efficacy is planned since the total number of subjects participating in this study is small (n=16).

5 STUDY POPULATION CHARACTERISTICS

5.1 Subject disposition

The number of subjects who received any study medication, completed, prematurely discontinued the study along with reasons for discontinuation, and the number of subjects re-induced in C87035 and in CR0012 will be summarized by dose group and overall for the Safety Population. In addition,

discontinuations due to AEs will be presented in a separate table. Disposition information will also be listed.

5.2 Protocol deviations

The number and percentage of subjects with at least one protocol deviation and the number and percentage of subjects by type of deviation (inclusion criteria, exclusion criteria, withdrawal criteria, prohibited medication use, incorrect dose received, treatment non-compliance, and procedural non-compliance) will be presented by dose group and overall. All protocol deviations will be listed.

6 DEMOGRAPHICS AND OTHER BASELINE CHARACTERISTICS

6.1 Demographics

Demographics will be summarized for the Safety Population by dose group and overall and will include age, age category (<12, ≥12 years), gender, race, ethnicity, height, weight, and body mass index (BMI). Note that for European Clinical Trials Database (EudraCT) regulatory requirements, age will also be presented categorically as (12 to <18, and 18 to 65 years). Demographic information will also be listed.

6.2 Medical history and concomitant diseases

Medical history and concomitant diseases will be coded according to the Medical Dictionary for Regulatory Activities (MedDRA, Version 20.1) and summarized for the Safety Population. The number and percentage of subjects by system organ class and preferred term will be presented. Medical history and concomitant diseases will also be listed.

Procedure history and concomitant medical procedures will not be coded and summarized in tabular form, but will be listed for the Safety Population.

6.3 Prior and concomitant medications

Prior and concomitant medication will be coded according to the WHO Drug Reference List (SEP/2017).

Medications will be separated into prior and concomitant medications. If the imputed start and stop dates of medication are before the date of first administration of study medication, the medication will be classified as a prior medication. Medications that were taken after start of CZP treatment or medications which started prior to the first administration of CZP treatment but are still ongoing at the time of first administration of CZP will be defined as concomitant medications.

Start dates will be imputed as follows:

- Missing day will be imputed as the first day of the month. Missing month will be imputed as January

Stop dates will be imputed as follows:

- Missing day will be imputed as the last day of the month. Missing month will be imputed as December

Concomitant medications will be summarized for the Safety Population. Tables will present the Anatomical Therapeutic Chemical classification system (ATC) anatomical main group (Level 2) and therapeutic/pharmacological subgroup (Level 4) by dose group and overall.

Prior and concomitant medications will be listed.

7 MEASUREMENTS OF TREATMENT COMPLIANCE

The number of weeks completed, number of expected doses, and number of doses received will be listed for the Safety Population. Definitions are provided below:

- Total weeks completed = $[(\text{last dose date} - \text{first dose date} + 1) / 7]$
 - If total weeks completed is <2 , then total expected doses = 0 since first study dose administration begins at the Week 2
- If the subject did not re-induce, then
 - total expected doses = $(\text{total \#weeks completed} / 4) + 1$ rounded down to the nearest integer
- If the subject did re-induce, then
 - total expected doses = $(\text{total \#weeks} / 4) + 2$ rounded down to the nearest integer

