7.7 Procedures for monitoring subject compliance

Subjects are expected to receive all doses of study drug as detailed in the schedule of assessments (Section 5.2). Any subject who deviates from the dosing schedule or misses any scheduled treatment should be reported to the Medical Monitor for determination of possible schedule adjustments and continued eligibility. These instances will be handled on a case-by-case basis.

At each visit after IMP is dispensed, subjects must return all unused IMP and empty IMP containers. Drug accountability must be done in the subject's presence in order to obtain explanations regarding discrepancies in compliance with the dosing regimen. Drug accountability must be recorded on the Drug Accountability form.

If a subject is found to be persistently noncompliant (missing 2 or more consecutive scheduled IMP doses or missing 3 or more doses), the Sponsor in conjunction with the Investigator will make a decision as to whether the subject should be withdrawn from the study.

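### SAP 7 ends the expected-dose count at the last injection received, so doses missed between that injection and withdrawal are left out

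*SAP*

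**What the plan says.** SAP 7 describes one output: "The number of weeks completed, number of expected doses, and number of doses received will be listed for the Safety Population". The number of weeks is defined as "Total weeks completed = $[(\text{last dose date} - \text{first dose date} + 1) / 7". For a subject who was not re-induced, expected doses are weeks divided by 4, plus 1, "rounded down to the nearest integer". For a re-induced subject the constant is 2 instead of 1. If the span is under 2 weeks, "then total expected doses = 0 since first study dose administration begins at the Week 2". No term uses the date of withdrawal, of the Completion/ET visit, or of a decision to stop treatment.

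Protocol 7.7 sets the standard against which doses are judged: "Subjects are expected to receive all doses of study drug as detailed in the schedule of assessments". It describes persistent non-compliance as "missing 2 or more consecutive scheduled IMP doses or missing 3 or more doses". In that event the sponsor, together with the investigator, "will make a decision as to whether the subject should be withdrawn from the study".

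Two other SAP sections bear on the point. Section 5.1 summarizes and lists reasons for discontinuation. Section 5.2 tabulates and lists protocol deviations by type, and treatment non-compliance is one of the types.

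**The concern.** The window for expected doses closes on the day of the last injection. Whatever the subject was due to receive after that day, while still in the study, falls outside it. The count therefore depends on whether the subject comes back: a gap in dosing is counted if an injection follows it and vanishes if none does.

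The error runs in one direction and falls on subjects who stop injecting before they leave. Such a gap is plausible here, because home dosing is allowed and regular clinic visits are 12 weeks apart, with phone calls between them. The primary objective is long-term safety and tolerability. SAP 4.4 gives 16 subjects, so one or two affected subjects would be a noticeable share of the listing. For the same subject, the section 7 listing could show no shortfall while section 5.2 records treatment non-compliance.

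**Working it through.** The documents give no numerical compliance figure to reproduce, so the SAP formula is applied to constructed dosing histories. They assume injections exactly 28 days apart, and that the last dose date means the last dose actually received.

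Formula: weeks = (last − first + 1)/7, in days. Expected = floor(weeks/4 + 1), or floor(weeks/4 + 2) after re-induction; expected = 0 if weeks < 2.

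**No missed doses.** Thirteen doses span 48 weeks: 337/7 = 48.14; 48.14/4 + 1 = 13.04; expected 13. Expected equals received for every on-schedule history from 2 to 99 doses, so the formula works when nothing is missed.

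**The same two misses, with and without a later dose.**

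| | Resumes | Does not resume |
|---|---|---|
| Doses given | Weeks 2 to 46, then 58 | Weeks 2 to 46 |
| Doses missed | Weeks 50, 54 | Weeks 50, 54; withdrawn at Week 58 |
| Weeks | 393/7 = 56.14 | 309/7 = 44.14 |
| Expected | floor(14.04 + 1) = 15 | floor(11.04 + 1) = 12 |
| Received | 13 | 12 |
| Actually due | 15 | 14 (Weeks 2 to 54) |

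In the second column the listing shows 12 and 12, while the true position is 12 of 14 (85.7%).

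**Number of misses after the last dose.** With 10 doses received and then 1, 2, 3 or 4 missed, the SAP gives 10 expected each time. The doses due are 11, 12, 13 and 14, so the true shares are 90.9%, 83.3%, 76.9% and 71.4%. With 2 received and 2 then missed, the listing shows 2 and 2 against 4 due.

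**Other patterns, 10 doses due.**
- Two consecutive misses, then the last scheduled dose given: 10 expected, 8 received. Visible in full.
- Three scattered misses, last scheduled dose given: 10 expected, 7 received. Visible in full.
- Two misses before the last injection and one after: 9 expected, 7 received (77.8% against a true 70.0%). Understated.
- One before and two after: 8 expected, 7 received (87.5% against 70.0%). Understated.

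**Edge cases.** One dose followed by misses gives weeks = 1/7 = 0.14, so 0 expected and 1 received. With an on-schedule re-induction, 11 doses received and 2 then missed: floor(36.14/4 + 2) = 11 expected, against 13 due (11/13 = 84.6%).

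The percentages are for scale only; SAP 7 lists counts.

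**The case against.** A reader might infer that every subject withdrawn under Protocol 7.7 would appear to have missed nothing. The documents do not support that. The protocol's criterion also covers three or more misses that need not be consecutive, and withdrawal is a case decision, so dosing may resume first. Misses followed by a later injection stay visible, and a one-dose subject shows 0 expected and 1 received. The full effect needs at least two doses received and every miss after the last injection.

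A reader might also take section 7 for the only compliance output. It is not: sections 5.1 and 5.2 should still show the discontinuation and the deviation. Nor does section 7 define a percentage, a threshold or a compliant label. Reading equal counts as full compliance is natural, but it is an inference. Neither document says how often subjects stop injecting before leaving, so nothing can be claimed about how common the pattern is.

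A larger example can be built: last dose at Week 50 and an ET visit at Week 74 gives 13 of 13 listed against 13 of 18 due (72.2%). It is strained. It needs 24 weeks off drug, beyond the Safety Follow-Up due 12 weeks after the last dose and well past the two-miss criterion.

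The best defence is that measuring adherence over the dosed interval, with discontinuation reported separately, is a recognised convention. There is also no Per Protocol set, no inferential efficacy analysis and no population that depends on this count. The point about limited consequences stands. The convention would be acceptable if declared, but the SAP presents the result as expected doses, and Protocol 7.7 expects all scheduled doses. SAP 8.1 does not define exposure duration, so it does not fill the gap.

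**Conclusion.** The point holds in a limited form. Under SAP 7, doses that fall due after the last injection are never expected. For a subject with at least two doses whose misses all follow the last injection, expected equals received however many were missed, as in 12 and 12 when 14 were due. Mixed patterns are understated, and misses before the last injection are shown correctly.

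Section 7 is the only planned count of expected against received doses, so the error is worth correcting even though it feeds no other analysis. The exact counts rest on 28-day spacing and on the natural reading of the last dose date, which the SAP does not define. Dosing within the ±7-day window can also shift the rounded count by one dose, which is a separate matter. How many of the 16 subjects are affected cannot be told from the documents.

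**What to change.** In SAP 7, replace the first-to-last-dose span with a count of scheduled doses:

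- **What counts.** All protocol-scheduled doses, meaning the Q4W doses plus the protocol-specified re-induction doses, from the first CR0012 injection. Counting Q4W doses alone would leave a fully dosed re-induced subject with more received than expected.
- **Where the count ends.** The earlier of the Completion/ET visit and, where recorded, the date of the decision to stop CZP. If neither exists, as may happen with loss to follow-up, use the last contact date.
- **When an ungiven dose is due.** Only if its visit window (+7 days) closed before the end date, so that an adherent completer is not charged with a miss. A scheduled dose that was given counts as expected in any case, so the under-2-weeks rule is no longer needed.
- **What is left out.** Doses withheld under a protocol-required interruption, such as the evaluation after TB contact in Protocol 9.6.5.

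In the example above, withdrawal at Week 58 then gives 14 expected and 12 received: the Week 54 window has closed and the Week 58 window has not.

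The cost is a short paragraph of SAP text and a small programming change. The sponsor should check whether a stop-decision date is captured, because Protocol 6.3 requires only the primary reason for withdrawal on the CRF. The downside is slightly lower listed compliance for subjects who stopped injecting before they left.
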